### **2.2.3 Description of Study Procedures**

Subjects must present to all study visits in the morning. Subjects must fast from all food and drink (except water) for a minimum of 12 hours prior to Visits 2 and 6 (12-hour fast is required for leptin analysis). Subjects must fast from all food and drink (except water) for a minimum of 8 hours prior to visits 1, 4, 5, 7, 9.

During treatment visits (Visits 3 through 9), when at the study site, subjects will have access to breakfast, lunch and dinner if appropriate. Subjects will eat breakfast or a morning snack (containing no more than 30% fat) after completion of all pre-dose assessments and just prior to

the time of dosing. Subjects will be instructed to take their dose of study medication at the clinic at each scheduled office visit (Visits 3, 4, 5, 7, 8). The date and time of dosing will be recorded at these visits.

### **Safety Assessments**

Physical Examinations: Physical examinations will be performed by a physician, or nurse practitioner or a physician's assistant. A complete physical examination will be performed at Screening (Visit 1). Genital, rectal, and breast examination may be excluded if not clinically indicated. Height and weight obtained at Screening (Visit 1) will be used to determine the BMI throughout the rest of the study. Weight will be collected at all other visits, excluding the phone call visits. A brief physical exam will be performed during Visit 2 to Visit 9, except for visit 3a.

Vital Signs: Vital sign measurements will include temperature, systolic and diastolic BP, heart rate (HR), respiratory rate (RR), and peripheral oxygen saturation (SpO2) after the subject has rested in a sitting position for at least 5 minutes. Vital sign measurements will be repeated if clinically significant or should machine/equipment errors occur. Out of range vital signs measurements will be repeated at the Investigator's discretion and documented in the case report form (CRF). Any confirmed, clinically significant, abnormal vital sign measurements must be recorded as adverse events.

12-Lead Electrocardiograms (ECG): An ECG machine with an automatic QTcF reporting feature will be utilized. 12-lead ECG will be obtained after the subject has rested in a fully supine position for at least 5 minutes. Because food can prolong QTc intervals which may be incorrectly attributed to CXA-10, subjects must refrain from eating or drinking for approximately 2 hours prior to obtaining ECGs except at screening. ECGs will be performed to determine eligibility to participate in the trial at Screening, and all other scheduled times prior to dosing. ECGs will be interpreted by a physician investigator experienced in interpreting ECGs. Additional ECGs may be performed if deemed medically appropriate.

Clinical Laboratory Tests: Clinical lab tests evaluation will include fasting glucose, comprehensive metabolic panel, fasting lipid profile, complete blood count, platelet and differential, and uric acid. In addition, HbA1C levels will be collected at Screening (Visit 1) on all subjects. Subjects with abnormal HbA1C at screening, will have blood collected for HbA1C levels at the end of the treatment period (Visit 6). PT/INR will be evaluated on all subjects as this is standard of care for anyone having a RHC. Patients who are on warfarin will return approximately one week after starting study drug to re-check PT/INR (Visit 3a).

Pulmonary Function Test (PFT): PFTs must be completed no more than 12 months before Screening or at Screening if outside the 12-month window. FEV1 and FVC parameters will be collected to determine eligibility to participate in the trial. Pulmonary function testing will be performed as per clinical standard of care.

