#### Study CXA-10-202

Oral administration of CXA-10 and placebo, at all doses, were safe and tolerated. There were no clinically significant abnormalities reported on physical examination, vital signs or routine ECG evaluation. CXA-10 at any dose had no clinically relevant effect on ECG parameters (i.e., HR, QTcF, PR, and QRS intervals) based on serial ECGs extracted from continuous 12-lead ECG recording (Holter monitoring). There were no clinically significant findings in clinical laboratory evaluations including CPK, Mg, creatinine levels, or LFTs. There were no significant findings in WBC counts including lymphocyte and monocyte counts. There was a slight decrease in hemoglobin and red blood cell (RBC) counts during treatment on Days 8 and 15 at the highest dose (450 mg) compared to placebo. There were no SAEs, withdrawals due to AEs, or deaths during the study.

A total of 26 out of 43 subjects who received CXA-10 across all dose groups or placebo reported AEs. The most commonly reported AEs (> 20%) were diarrhea, nausea, presyncope, fatigue and back pain. More subjects in the 450-mg dose group (cohort 3) reported AEs of diarrhea and nausea. The Investigator considered AEs of diarrhea, nausea, presyncope, and fatigue as possibly or definitely related to study medication. The AEs of back pain were considered unrelated by the Investigator. All reported AEs were mild to moderate in intensity and all resolved without sequelae.

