After 12 weeks of study treatment, subjects will return for a repeat right heart catheterization, in addition to all study endpoints. PK samples and plasma NT-proBNP will be collected. All subjects, regardless of whether they completed study treatment or discontinued study treatment prematurely, will be asked to return for a safety follow-up visit (4 weeks after stop of study medication intake). Additional follow-up assessments by telephone will occur in between each outpatient clinic visit at Weeks 2, 6 and 10.

Throughout the study, subjects will be monitored carefully for occurrences of adverse events, laboratory test abnormalities, and changes in vital signs. The expected duration of each subject's participation in this proposed clinical investigation is approximately 5 months.

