#### Visit 2 (Week 0- Baseline testing)

This visit will take place at UPMC Montefiore. Subjects will be asked to fast a minimum of 12 hours to perform the assessments listed below.

- Brief physical exam with a body weight measurement and WHO Functional class assessment
- Vital signs (temperature, blood pressure, respiratory rate, heart rate, and pulse oximetry measurements are taken).
- ECG
- Echocardiogram (this test may be completed at any visit prior to first dose of drug)

- Clinical laboratory tests and urinalysis (fasting glucose, comprehensive metabolic panel, fasting lipid profile, CBC/Diff/Plt, uric acid, PT/INR)
- Research blood samples for biomarkers, cytokines measurements NT-proBNP
- Urine pregnancy test for female child-bearing potential
- IVGTT
- Health related quality of life questionnaire - Pulmonary Arterial Hypertension-Symptoms and Impact (PAH-SYMPACT®)
- Return accelerometer for data download
- Concomitant medications assessment
- AE assessment

Visit 3 (Week 0 – First dose)

This visit will take place at UPMC Montefiore. Subjects do not need to fast for this visit and this visit will last up to about 4 hours.

- 6MWT
- Blood draw for Population PK sampling (pre-dose and 2-4 hours after taking the study drug)
- Research blood samples for biomarkers, cytokines measurements (samples collected at the same times as PK samples)
- Subjects will be instructed to take the first dose of study medication at the clinic after a breakfast/morning snack containing up to approximately 30% fat
- Dispense study drugs
- Concomitant medications assessment
- AE assessment

Visit 3a (Week 1: +3d)

This visit will take place at UPMC Montefiore or UPMC Presbyterian. This visit will last approximately 30 minutes. Subjects who are on warfarin will be asked to return to the clinic one week after taking the study drug for a blood draw for PT/INR. If the INR value is > 2.5, the warfarin dose may be adjusted per the standard of care. Subjects do not need to fast for this visit.

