## 2.5 STATISTICAL ANALYSIS

### 2.5.1 Sample Size Determination

We plan to enroll 30 subjects with PAH, allowing for a conservative drop-out rate of 10%, in this open label trial of oral CXA-10. We expect to see decrease in the PVR after 12 weeks of therapy. The intention to treat (ITT) population will consist of all subjects who have received at least one dose of study medication. To estimate our effect size for power calculations, we use data from the SUPER-1 sildenafil PAH trial (a randomized placebo control trial evaluating the effects of 20 mg, 40 mg or 80 mg TID of sildenafil in subjects with PH). Using the hemodynamic data from the 80 mg arm of the SUPER-1 trial and making a conservative assumption that our therapy will only have an effect that is 70% of sildenafil (decrease in PVR of 2.3 woods units with SD of 4.1), the sample size required for 80% power and P = 0.05 is 27 subjects (Table 2). We anticipate more than sufficient power to detect vasodilatory effects of NO2-OA administration (decreased PVR) after 3 months of therapy. Based on our extensive phase 1 data with CXA-10 formulations, we

anticipate the drug will cause no systemic blood pressure changes and no increases in methemoglobin levels.

**Table 2 Required sample size for different effect,  
Power =0.8 ,  $\alpha=0.05$ , two sided test**

% of Sildenafil	Mean (SD) PVR change, Woods unit	N
90	3.0 (4.9)	23
80	2.6 (4.2)	23
70	2.3 (4.1)	27

With safety as the primary outcome measure, we use Fleming's single stage phase II design with the following assumptions:  $\alpha = 0.05$ , Power= 0.80, lower proportion for rejection 70% (with no SAEs), higher proportion of acceptance 90% (with no SAEs) with maximum recruited patients of 27 patients resulting in a minimum number of success (with no SAEs to indicate that the treatment is safe) is 24. Thirty patients will be enrolled to compensate for up to 10% lost-to follow-up.

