#### **6.4.8. Withdrawal of Subjects and Stopping Criteria:**

##### **STOPPING RULES:**

**Dose Reduction:** If subjects experience an increase of  $\geq 7$  stools/day over baseline or any serious AE believed to be possibly related to the study drug the dose of the study drug may be reduced to 150 mg/day or 75 mg/day at the discretion of the physician investigator. Subjects may be asked to return to the clinic for an unscheduled visit to assess their status if deemed necessary

based on the clinical judgement of the physician investigator. This unscheduled visit may require blood draws, vital signs and/or review of concomitant medication.

**Withdrawal of Subjects:** Subjects must be withdrawn from the study for the following reasons:

- Systolic BP < 80 mmHg
- Liver function test abnormalities: if ALT and/or AST > 8X ULN, the subject should stop taking study drug immediately. Medical evaluation should be undertaken as appropriate to the signs and symptoms manifested by the subject
- Positive pregnancy test

Subjects may be withdrawn from the study for the following reasons:

- At their own request
- At the specific request of the Investigator (eg: detection of a new significant safety concern related to the study drug)
- Occurrence of intercurrent diseases which in investigator's opinion, continuation of the study drug would be harmful to the subject's well-being
- Pertinent non-compliance with the conditions for the trial or instructions by the investigator
- Lost to follow up

Any subject removed from the study will remain under medical supervision until the condition is medically acceptable. Study subjects removed from the study will be replaced by enrolling another volunteer with similar demographics.

Subjects not completing the entire study should be fully evaluated when possible according to the following schedule:

- If study medication is discontinued on or prior to Week 4, complete all protocol required assessments scheduled for the End of Treatment visit excluding the RHC.
- If study medication is discontinued after Week 4 but prior to Week 10, complete all protocol required assessments scheduled for the End of Treatment visit excluding the RHC.
- If study medication is discontinued on or after Week 10 and prior to the start of the End of Treatment visit, complete all protocol required assessments scheduled for the End of Treatment Period.

All withdrawn subjects will be asked to report to the clinic for a follow-up visit (Visit 9).

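### No clinic vital-sign set in the 12-week period is specified as post-dose, and the first-dose clinic visit (Visit 3) schedules none at all

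*Combined protocol and SAP*

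**What the plan says.** - **ECG timing.** Section 2.2.3 (Safety Assessments) states: "ECGs will be performed to determine eligibility to participate in the trial at Screening, and all other scheduled times prior to dosing". The vital-signs paragraph beside it sets posture and rest but is silent on time since dose.
- **Vital-sign schedule.** Section 2.2.2 and Appendix A place clinic vital signs at Visits 1, 2, 4, 5, 6 and 9. There is no entry at Visits 3, 7 or 8.
- **Visit 3.** The section 2.2.2 text reads: "Subjects do not need to fast for this visit and this visit will last up to about 4 hours". The list has a walk test, blood draws before and 2 to 4 hours after the dose, the dose itself, dispensing, concomitant medications and AE review. It has no vital signs.
- **Cath lab.** Under section 2.2.1 the first 10 subjects take their first dose at the Visit 1 catheterization, repeated at Visit 7, with hemodynamics 30 minutes after dosing. Section 2.2.2 adds automated blood pressures at intervals during catheterization.
- **What depends on these readings.** Section 2.2.1 undertakes that "subjects will be monitored carefully for occurrences of adverse events, laboratory test abnormalities, and changes in vital signs". Section 2.2.3 adds: "Any confirmed, clinically significant, abnormal vital sign measurements must be recorded as adverse events". Section 2.4 makes the incidence of treatment-emergent adverse events the primary endpoint. Section 6.4.8 lists "Systolic BP < 80 mmHg" as a mandatory withdrawal reason, with no measurement time. In section 2.5.1 the investigators "anticipate the drug will cause no systemic blood pressure changes and no increases in methemoglobin levels".

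**The concern.** Safety is the main objective, and blood pressure reaches the primary endpoint only if someone measures it or the subject has symptoms. If the scheduled readings are taken before the day's dose, they fall roughly a day after the previous one. They then say little about the hours after dosing, in patients who by the inclusion criteria are already on PAH therapy, which section 1.3.1 describes as vasodilating or as inhibiting vasoconstriction. The withdrawal criterion and the expectation of no systemic blood-pressure change would be only thinly tested in that window. The gap is avoidable: subjects are already in clinic for post-dose blood draws at Visits 3, 4, 5 and 8.

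**Working it through.** The plan states no figure on this point, so the first check is a comparison of passages.

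**1. Where dosing and vital signs coincide.** Section 2.2.3 names Visits 3, 4, 5, 7 and 8 for in-clinic dosing.

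| Visit | Post-dose blood draw | Clinic vital-sign set | Timing of set relative to dose |
|---|---|---|---|
| 3 | 2-4 h | none | n/a |
| 4 | 2-4 h | yes | not stated |
| 5 | 2-4 h | yes | not stated |
| 6 | none | yes | not stated; no dose in the visit list |
| 7 | 4-6 h | none (cath-lab pressures only) | n/a |
| 8 | 4-6 h | none | n/a |

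This gives three on-treatment sets per subject, none specified as post-dose, and sets at two of the five in-clinic dosing visits.

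**2. Likely timing at Visits 4 and 5.** Section 2.2.2 has subjects arrive undosed for a pre-dose assessment. Section 2.2.3 puts pre-dose assessments first, then food, then the dose. Pre-dose is therefore the likely reading, but it is an inference.

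**3. Who has a planned post-dose pressure.** The Appendix A footnote limits the acute evaluation to the first 10 enrolled. Section 2.1 plans about 30, so 30 - 10 = 20 subjects (20/30 = 67%) have no scheduled post-dose blood pressure on that reading. The 10 have it on up to two occasions. Coverage at Visit 1 may be lower, because a clinical catheterization within 2 months can replace the screening one. The specified 30-minute point precedes the plan's own 2-4 h and 4-6 h sampling windows.

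**4. Scale (illustration only).** The documents give no rate of post-dose blood-pressure falls. Let p be an assumed, independent per-subject probability that a post-dose reading shows one. Then P(at least one seen) = 1 - (1 - p)^n.

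| p (assumed) | n = 10 | n = 30 |
|---|---|---|
| 2% | 18.3% | 45.5% |
| 5% | 40.1% | 78.5% |
| 10% | 65.1% | 95.8% |
| 20% | 89.3% | 99.9% |

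For example, at p = 10%: 1 - 0.9^10 = 0.651 and 1 - 0.9^30 = 0.958.

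If no case is seen, the one-sided 95% upper bound on p is 1 - 0.05^(1/n): 25.9% for n = 10 and 9.5% for n = 30.

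**5. Passages that disagree.**
- Section 2.2.3 calls for a brief exam at Visits 2 to 9 (except 3a) and weight at every visit other than calls. The Visit 3 list has neither.
- The Visit 7 list gives the 30-minute measurement without the first-10 limit that the Appendix A footnote states.
- Section 2.3.2 starts dosing at Visit 3, while section 2.2.1 gives the first 10 subjects a dose at Visit 1.
- Section 2.3.2 has the Visit 6 dose given in clinic, while section 2.2.3 omits Visit 6.

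**The case against.** The strongest reply is that the plan is not blind after dosing. Ten subjects have cath-lab pressures at the first dose and again at Week 12, and the Visit 7 text could be read as covering everyone. Symptomatic events can reach the record through home logging of dose times and symptoms, telephone calls and AE review. All of this stands. A reader might infer that post-dose effects are missed outright, or that the current plan would see essentially no cases. The documents do not support that: even at an assumed 10% rate, 10 subjects give a 65.1% chance of seeing one. What remains uncovered is the asymptomatic fall outside that group. The cath-lab readings also differ in kind. They are supine, sedatives may be used (section 6.1), and systemic pressure is not among the named catheterization parameters for analysis.

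Earlier human data are also reassuring. A reader might point to the line on CXA-10-202, "The most commonly reported AEs (> 20%) were diarrhea, nausea, presyncope, fatigue and back pain", with presyncope judged possibly or definitely drug-related. But that list pools all doses with placebo, and the same account reports no clinically significant vital-sign abnormality. No passage documents an acute blood-pressure effect, so a claim that the adverse-event rate is biased toward zero would go too far. The formal rule in section 2.5.1 counts subjects without SAEs (24 of 27), which an asymptomatic transient reading would rarely change.

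A reader might also extend the point to ECGs and ask for one to be moved after the dose. That does not follow. Section 2.2.3 gives a reason linked to food and QTc, allows extra tracings ("Additional ECGs may be performed if deemed medically appropriate"), and CXA-10-202 included serial ECGs with no relevant effect. Moving one would also lose a pre-dose comparison with Visit 2.

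**Conclusion.** The point holds as a gap in specification and coverage. No clinic vital-sign set in the 12-week period is specified as post-dose, and Visit 3 has none. About 20 of 30 subjects therefore have no scheduled post-dose blood pressure if the acute evaluation is limited to the first 10. It would be wrong to say that the plan places all vital signs before the dose: that is explicit only for ECGs, and likely but unwritten for Visits 4 and 5.

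The gain from wider coverage depends on an assumed rate. At 5% the chance of seeing at least one case rises from 40.1% to 78.5%; with no cases, the upper bound falls from 25.9% to 9.5%. The illustration treats a reading at 30 minutes and one at 2 to 4 hours as equally informative. The documents give no time to peak concentration or effect, so neither window can be called better. This is a worthwhile, inexpensive improvement to safety capture, and it does not undermine the trial's formal safety rule.

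**What to change.** In section 2.2.2 and Appendix A:

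1. Add the existing seated vital-sign set at Visit 3, before the dose and at the 2-4 h draw.
2. Add the same set at the post-dose draws already scheduled at Visits 4, 5 and 8.
3. Label the present Visit 4 and 5 sets as pre-dose, and state timing relative to dose in the section 2.2.3 vital-signs paragraph.
4. Reconcile the Visit 3 list with section 2.2.3 on the brief exam and weight, and the Visit 7 list with the Appendix A footnote on who has the post-dose measurement. Reconcile also the passages on where dosing starts and whether Visit 6 includes a clinic dose.

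Leave ECG timing, doses and the withdrawal threshold as they are. The cost is a few minutes at each of four visits, new schedule marks and extra CRF fields, with no new visit, staff or equipment. The downside is slightly more reported vital-sign adverse events.

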#### Pharmacokinetic Results

Based on the results of the CXA-10-203 exploratory drug-drug interaction study, there is a potential for a drug-drug interaction with CXA-10 and simvastatin. This interaction results in increased exposure of the metabolite of simvastatin (simvastatin hydroxy acid), indicating that OATP1B1 may be inhibited by CXA-10. Simvastatin hydroxy acid is more potent than parent simvastatin. As a result, co-administration of CXA-10 and simvastatin could result in greater risk for side effects commonly associated with statins, including increased CPK, muscle toxicity, and liver function test elevation. In the absence of a definitive drug-drug interaction study, clinical studies involving CXA-10 will not allow the concomitant use of simvastatin at doses exceeding 20 mg daily.

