The rationale for PT/INR measurement in PAH patients on warfarin is that Warfarin is a substrate of CYP2C9. Although the concentrations of CXA-10 *in vivo* are significantly lower than the concentrations *in vitro*, CXA-10 has shown moderate *in vitro* inhibition of CYP2C9. The lowest IC50 value, based on *in vitro* inhibition for CYP2C9, was 2.2  $\mu$ M. The peak plasma concentrations of CXA-10 in humans following oral administration of a 1200 mg dose were less than 10 ng/mL (< 30 nM). Modeling of CXA-10 direct CYP inhibition *in vitro* data for CYP2C9 is projected to yield an R1 value (R1 = 1+[I]/Ki) of 1.02 for CYP2C9, that is less than the R1 value of 1.1, as defined in FDA Guidance Industry February 2012. Therefore, CXA-10 is not expected to increase the exposure to concurrently administered drugs that are primarily cleared by CYP2C9-mediated elimination mechanisms. Even though the potential for a drug-drug interaction is low, we will measure PT/INR on Week 2 for subjects taking warfarin. CXA-10 must reach steady-state concentration before collecting blood for PT and steady state of CXA-10 is achieved by day 7.

Visit 4 (Week 4;  $\pm$  5d) and Visit 5 (Week 8;  $\pm$  5d)

Subjects will report to the clinic on the morning of Week 4 and Week 8 (Visit 4 and Visit 5) after a minimum 8-hour overnight fast. Subjects should not take their study medication that morning, prior to arriving at the clinic for their pre-dose assessment.

- Brief physical exam
- Body weight
- ECG
- Vital signs (temperature, blood pressure, respiratory rate, heart rate, and pulse oximetry measurements are taken).
- Clinical laboratory testing and urinalysis (fasting glucose, comprehensive metabolic panel, fasting lipid profile, CBC/Diff/Plt, uric acid)NT Pro-BNP
- Urine pregnancy test in women of childbearing potential
- 6MWT with Borg Dyspnea Scale
- Health related quality of life questionnaire - PAH-SYMPACT®
- WHO Functional Class assessment
- Dispense study drugs. Subjects will be instructed to take the study medication at the clinic after a breakfast/morning snack containing up to approximately 30% fat
- PK blood sampling (pre-dose and 2-4 hours post-dose)
- Research blood samples for biomarkers, cytokines measurements (samples collected at the same times as PK samples)
- Concomitant medications assessment
- AE assessment
- Provide accelerometer on week 8 only and instruct to wear the accelerometer for at least 7 consecutive days prior to the next visit (Week 12).

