### **Efficacy Assessments**

Right Heart Catheterization (RHC): RHC is performed routinely as a clinical standard of care procedure for diagnostic purposes in this population. RHC will be performed at Screening and at the end of the treatment (Visit 6 – Week 12).

Briefly, RHC will be performed with a balloon tipped, flow-directed, pulmonary artery catheter (e.g. 7F Swan Ganz catheter) inserted through a sheath in the internal jugular vein under continuous

ECG monitoring. An alternate vein may be used at the physician's discretion. All measurements will be recorded with the subject in a supine position, at rest, breathing room air or with supplementary oxygen to obtain peripheral saturations above 90%. Hemodynamic recording of right atrial, right ventricular, pulmonary artery pressures, pulmonary artery wedge pressure and cardiac output will be made. Parameters for analysis will include: Mean RAP, RVSP, RVDP, PASP, PADP, Mean PAP, Mean PAWP, Thermodilution Cardiac Output, PVR, Cardiac Index, and Pulmonary Vascular Compliance. Mixed venous oxygen saturation (SvO2) will be determined from a sample drawn from the Swan-Ganz catheter. Other parameters may be obtained as data permit.

**Echocardiogram:** Noninvasive transthoracic echocardiograms will be completed to assess RV function by measures such as tricuspid annular plane systolic excursion (TAPSE) as well as tissue Doppler of the lateral tricuspid valve anulus (S').

**Six Minute Walk Distance Test and Borg Dyspnea Scale:** The 6MWD test will be performed according to a protocol-specific modification of the American Thoracic Society guidelines. The 6MWD test measures the distance an individual is able to walk over a total of six minutes on a hard, flat surface. The Borg Scale is a method of rating perceived exertion during exercise. It should be performed immediately after the 6MWD test.

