## **3.2 INCLUSION CRITERIA**

The following criteria will be required on ALL subjects:

- Male or female between 18-80 years of age inclusive at Screening
- Weight  $\geq$  40 kg or 88 lbs
- Have a WHO Classification of Functional Status Class II or III
- Must meet all of the following hemodynamic criteria by means of a right heart catheterization: mPAP of  $\geq$ 25 mmHg, PVR  $\geq$  3 wood units, PAWP of  $\leq$ 15 mmHg. A clinical RHC done within 2 months is acceptable to determine eligibility
- Meet all of the following pulmonary function test parameters, completed no more than 12 months before Screening or at screening: forced expiratory volume in one second (FEV1)  $\geq$  60% of predicted normal and forced vital capacity (FVC)  $\geq$  60%
- A 6 MWD test of  $\geq$  100 m and  $\leq$  600 m at Screening
- Participants enrolled in an exercise program for pulmonary rehabilitation must be in a stable program 1 month prior to Screening and must agree to maintain their current level of rehabilitation throughout the study. If subjects are not enrolled in an exercise training program for pulmonary rehabilitation they cannot enroll during the Screening/Baseline Period or throughout the study
- If receiving 3-hydroxy-3-methyl-glutaryl-coenzyme A (HMG-CoA) reductase inhibitors (i.e., statins) subjects must not have changed their dose  $<$ 4 weeks prior to Screening
- If receiving simvastatin-containing products: simvastatin (Zocor), Vytorin, or any other combination therapy containing simvastatin, the subject's simvastatin dose should not exceed 20 mg/day  
Note: Subjects using a simvastatin product at dose  $>$  20 mg/day may be rescreened if their dose has been adjusted to  $\leq$  20 mg/day, at least 4 weeks prior to Screening with no dose or regimen changes within 4 weeks prior to Baseline
- Subjects must be receiving one or more of the following previously approved PAH therapies: phosphodiesterase type 5 inhibitors (PDE5), endothelin receptor antagonist (ERA), soluble guanylate cyclase (sGC) stimulator, prostanooids, prostacyclin receptor agonists and must be on stable doses ( $\geq$  3 months) with no dose adjustment within 1 month of Screening
- Ability to provide written informed consent

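### No scheduled lab list includes CPK, so a symptom-free CPK rise from the permitted simvastatin co-medication cannot be assessed from the planned data

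*Combined protocol and SAP*

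**What the plan says.** Section 1.3.3 (Pharmacokinetic Results) reports that CXA-10 may increase exposure to simvastatin hydroxy acid, a metabolite described as more potent than simvastatin itself. It names three possible consequences, "including increased CPK, muscle toxicity, and liver function test elevation". The stated control is a dose limit. Section 3.2 requires that "the subject's simvastatin dose should not exceed 20 mg/day", and Section 2.3.7 and the drug table in Section 3.4.1 repeat the limit for the treatment period.

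Section 2.2.3 (Safety Assessments) defines the laboratory panel: "Clinical lab tests evaluation will include fasting glucose, comprehensive metabolic panel, fasting lipid profile, complete blood count, platelet and differential, and uric acid". HbA1C and PT/INR are added at some visits. The on-treatment list for Weeks 4 and 8 in Section 2.2.2 has the same content: "Clinical laboratory testing and urinalysis (fasting glucose, comprehensive metabolic panel, fasting lipid profile, CBC/Diff/Plt, uric acid"). Appendix A carries one generic row for clinical labs and urinalysis, marked at Visits 1, 2, 4, 5, 6 and 9. The Open Label Period text repeats the chemistry at months 4 and 6.

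Safety is the main objective (Section 1.1), and treatment-emergent adverse events are the primary endpoint (Section 2.4). Section 2.5.2 evaluates safety partly through laboratory changes: values are compared with normal ranges, flagged if of concern, and shown as changes from baseline.

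**The concern.** The protocol describes an interaction, names a CPK rise as one of its consequences, permits the interacting drug, and then schedules no CPK. The three oral Phase 1 summaries in Section 1.3.3 (CXA-10-201, -202 and -203) all report CPK, so an analyte tracked there has been dropped in a longer study in patients.

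At stake is one part of the safety description. If CPK rose in simvastatin users without muscle symptoms, no scheduled test would show it, nothing could be flagged under Section 2.5.2, and the final report could not say whether it happened. This trial would be a natural source of such data, because Section 1.3.3 concedes that no definitive interaction study exists.

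**Working it through.** The plan gives no figure on this point, so there is none to reproduce. The check is mainly a comparison of passages.

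**1. Is CPK anywhere in the schedule?** The lists checked were Visits 1, 2, 4, 5, 6 and 9 and the Open Label Period (Section 2.2.2), the general definition (Section 2.2.3) and Appendix A with its footnotes. CPK is in none of them. It appears only in Section 1.3.3, in the Phase 1 summaries and the interaction warning. The metabolic panel is not itemized. I take CPK to lie outside it because the Phase 1 summaries list CPK separately from creatinine and liver function tests.

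**2. How is each named consequence covered?**

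| Consequence named in Section 1.3.3 | Planned laboratory measure | Other route |
|---|---|---|
| Liver test elevation | Metabolic panel at six visits; Section 6.4.8 has an ALT/AST withdrawal rule, which presupposes the tests | Adverse event |
| Muscle toxicity | None | Adverse event, if symptomatic, at nearly all clinic and telephone contacts |
| CPK increase | None | None planned |

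Section 6.4.8 allows blood draws at unscheduled visits, but it does so in the context of the dose-reduction triggers (severe diarrhea or a possibly related serious event) and names no tests.

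**3. Does the 20 mg limit answer the gap?** Inputs are from Sections 1.3.3, 2.3 and 2.3.5.

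- Simvastatin dose: 20 mg in CXA-10-203 (within Vytorin), up to 20 mg here. Ratio 20/20 = 1.
- CXA-10 dose: 150 mg daily there, 300 mg daily here. Ratio 300/150 = 2.
- Simvastatin doses taken with CXA-10: one there, after 9 days of CXA-10; up to 12 × 7 = 84 daily doses here, before any 6-month extension.

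The limit holds simvastatin at the dose already studied, while CXA-10 dose and duration of co-exposure both go up.

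**4. How does the plan treat its other flagged interaction?** For warfarin, Section 2.2.2 projects R1 = 1.02, below the cited threshold of 1.1, and expects no effect. It still adds Visit 3a to check PT/INR. For simvastatin, Section 3.4.1 treats the effect as shown, yet no muscle marker is added.

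**5. What would measurement buy?** The documents give neither the number of simvastatin users, m, nor a CPK-elevation rate, q. Purely as assumptions, take m = 3, 6 or 9 (10%, 20% or 30% of 30 subjects) and q = 5% or 10%. The chance that at least one case exists to be found is 1 − (1 − q)^m. With no case observed, the one-sided 95% upper bound on the rate is 1 − 0.05^(1/m).

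| m | At least one case, q = 5% | At least one case, q = 10% | Upper bound if none seen |
|---|---|---|---|
| 3 | 1 − 0.95³ = 14.3% | 1 − 0.90³ = 27.1% | 1 − 0.05^(1/3) = 63.2% |
| 6 | 26.5% | 46.9% | 39.3% |
| 9 | 37.0% | 61.3% | 28.3% |

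If CPK were measured in all 30 subjects and none rose, the bound over all subjects would be 1 − 0.05^(1/30) = 9.5% (10.5% for 27). With no CPK test scheduled, planned labs find none of these cases and give no bound. With m = 0 the interaction question does not arise in this trial.

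**The case against.** The best defense is that the protocol already manages this risk and that the evidence so far is reassuring. The simvastatin limit is applied consistently, Section 3.2 requires a stable statin dose before screening, and Section 3.4.1 points to an alternative statin. CPK was measured in the three Phase 1 studies, including the interaction study, and nothing clinically significant was found. That covers single doses up to 1200 mg, 1800 mg divided, and 450 mg daily within a 14-day course. Two of the three named consequences have a route into the data. The decision rule in Section 2.5.1 counts subjects without serious adverse events, which a symptom-free CPK rise would not ordinarily change.

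All of this stands, and it limits the weight of the point. It does not supply a CPK value. The reassuring interaction result comes from a single simvastatin dose with half this trial's CXA-10 dose, and the limit is that same simvastatin dose.

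Two stronger readings are tempting. A reader might infer that the trial would be blind to the interaction altogether. It would not, since liver tests are measured and muscle symptoms can be reported. A reader might also put methemoglobin beside CPK, because Section 2.5.1 anticipates "no systemic blood pressure changes and no increases in methemoglobin levels" and no assay is planned. That is a passing expectation in the sample-size text. Methemoglobin is not an endpoint in Section 2.4 or a listed drug risk in Section 6.1, and no analysis depends on it. Nor would the mixed venous sample from catheterization always be available for such a test: the Visit 1 procedure can be skipped if one was done within 2 months, and subjects who stop before Week 10 have none at the end.

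**Conclusion.** The point holds in a limited form. The protocol names a CPK rise as a consequence of an interaction with a drug it permits, and no scheduled test can show that rise unless it comes with symptoms. The dose limit does not answer this, because it keeps the simvastatin dose already studied while CXA-10 is doubled and co-exposure lengthened.

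The size is modest and cannot be fixed from the documents. It depends on how many subjects take simvastatin, possibly none, and on an elevation rate for which the documents give no estimate. It does not affect the efficacy analyses or, ordinarily, the serious-event rule. It bears on the completeness of the laboratory safety description in a trial whose main objective is safety. The conclusion assumes that CPK is not part of the site's metabolic panel; if it is, the protocol need only say so.

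**What to change.** Add CPK to the chemistry already drawn at Visits 1, 2, 4, 5, 6 and 9 and at open-label months 4 and 6, in Sections 2.2.2 and 2.2.3 and in Appendix A. Testing all subjects is preferable, since non-users give a background rate in a single-arm trial; statin users are the minimum. In Section 2.5.2, summarize CPK as for the other labs, with change from baseline, and show simvastatin users separately. How a raised value is acted on is for the investigators and is not proposed here.

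The cost is one analyte on samples already taken, with no added visit: at most 30 × 6 = 180 assays in the main study and 30 × 2 = 60 in the extension. The downside is occasional nonspecific elevations that need follow-up.
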